#### 4.5.1. Extent of Exposure

Summary of duration of follow-up (defined as time in days from date of randomization to the date of the last study visit) and/or duration on study treatment (defined as time in days from date of first dose of study treatment to date of last dose of study treatment plus 7 days) will be provided by treatment group using data from SS.

For the summary of duration on study and study treatment, the frequency and percentage of participants falling into the following range will be summarized by planned treatment group as well:

- >()
- ≥4 weeks
- >8 weeks
- ≥12 weeks
- >16 weeks
- >20 weeks

- >24 weeks
- >36 weeks
- >48 weeks
- ≥52 weeks
- >72 weeks

In addition, the frequency and percentages of participants falling into the following exposure ranges for study and study treatment may be summarized by planned treatment group:

- 0 weeks
- >0 to <4 weeks
- >4 to <8 weeks
- >8 to <16 weeks
- $\geq$ 16 to  $\leq$ 24 weeks
- >24 to <36 weeks
- >36 to <48 weeks
- >48 to <52 weeks
- >52 to <72 weeks
- >72 weeks

No p-values will be reported in these summaries as they are intended to describe the study populations, rather than test hypotheses about them.

#### 4.5.2. Adverse Events

# **4.5.2.1.** Treatment Emergent Adverse Events

A TEAE is defined as an event that first occurred, or worsened in severity, after baselines defined in Table GPHZ.4.1. The MedDRA LLT will be used in the treatment-emergent derivation. The maximum severity for each LLT during the baseline period, including ongoing medical history, will be used as baseline severity. For events with a missing severity during the baseline period, it will be treated as "mild" in severity for determining treatment-emergence. Events with a missing severity during the postbaseline period will be treated as "severe", and treatment-emergence will be determined by comparing to baseline severity.

For events occurring on the day of first taking study medication, the CRF-collected information (e.g., treatment emergent flag, start time of study treatment and event) will be used to determine whether the event was pre- versus post-treatment, if available. If the relevant information is not available, then the events will be counted as post-treatment.

The counts and percentages of participants with TEAEs will be summarized by treatment using MedDRA PT nested within SOC. Statistical comparisons will be applied at both the SOC and PT levels. Events will be ordered by decreasing frequency within SOC. SOC will be presented in alphabetical order. For events that are sex-specific, the denominator and computation of the percentage will include only participants from the given sex.

An overview of the number and percentage of participants who experienced a TEAE, TEAE related to study treatment, SAE, death, or discontinued from study and/or study treatment due to an AE will be summarized by treatment.

The counts and percentages of participants with TEAEs by maximum severity will be summarized by treatment using MedDRA PT. For each participant and TEAE, the maximum severity for the MedDRA PT is the maximum postbaseline severity observed from all associated LLTs mapping to the MedDRA PT. The maximum severity will be determined based on the non-missing severities. If all severities are missing for the defined postbaseline period of interest, it will show as missing in the table.

#### 4.5.2.2. Common Adverse Events

The counts and percentages of participants with TEAEs, overall and common (common TEAEs occurred in  $\geq$ 5% of participants in any treatment group before rounding), will be summarized by treatment using MedDRA PT. Events will be ordered by decreasing frequency.

# 4.5.3. Additional Safety Assessments

#### 4.5.3.1. Deaths

A listing of all deaths during the study will be provided. The listing will include participant identification including the treatment, site number, date of death, age at the time of enrollment, sex, time from last dose of study drug to death (if participant had discontinued study drug), and primary cause of death.

#### 4.5.3.2. Other Serious Adverse Events

The counts and percentages of participants who experienced an SAE (including deaths and SAEs temporally associated with or preceding deaths) during the postbaseline period will be summarized by treatment using MedDRA PT nested within SOC. Events will be ordered by decreasing frequency within SOC. The SOC will be in alphabetical order.

A listing of all SAEs will be provided. The listing will include treatment, participant identification including the site number, date of event, age at the time of enrollment, sex, MedDRA SOC and PT, AE start date, AE end date, severity, action taken related to study treatment, outcome, relationship to study drug, and the last dose date of study drug.

#### 4.5.3.3. Other Significant Adverse Events

The counts and percentages of participants who discontinued from study drug or study due to an AE during the postbaseline period may be summarized by treatment group using MedDRA PT nested within SOC. Events will be ordered by decreasing frequency within SOC.

Parameter Low High Systolic BP (mm Hg) ≥140 and increase from baseline (Supine or sitting –  $\geq 20;$ <90 and decrease from baseline >20 forearm at heart level) >129 and increase from baseline Diastolic BP (mm Hg) (Supine or sitting –  $\leq$ 50 and decrease from baseline  $\geq$ 10  $\geq$ 90 and increase from baseline  $\geq$ 10 forearm at heart level) Pulse (bpm) <50 and decrease from baseline >15 >100 and increase from baseline ≥15 (Supine or sitting)

Table GPHZ.4.5. Categorical Criteria for Abnormal Treatment-Emergent Blood Pressure and Pulse Measurements

Abbreviations: BP = blood pressure; bpm = beats per minute.

## 4.5.3.5. Electrocardiograms

Summary statistics by treatment and by nominal visit will be provided for ECG parameters (heart rate, pulse rate [PR], QRS, QT, and QT corrected using Fridericia's correction factor [QTcF = QT / RR0.333]). When the QRS is prolonged (e.g., a complete bundle branch block), QT and QTc should be used to assess ventricular repolarization. Thus, for a particular ECG, the following will be set to missing (for analysis purposes) when QRS is  $\geq$ 120 msec: QT and QTcF.

Change from baseline to postbaseline values for ECG parameters will be summarized for participants who have both a baseline and at least 1 postbaseline result. Treatment differences in mean change from baseline for heart rate and PR will be assessed using the analysis model described in Section 4.3.2.1. Only planned measurements will be included in the mean change analyses.

The counts and percentages of participants who meet following criteria at any time during the entire study period (including the safety follow up time period) will be summarized by treatment group:

- treatment-emergent ECG abnormalities as listed in Table GPHZ.4.6.
- QT greater than 500 msec
- QTcF greater than 500 msec, and

• treatment-emergent increase from the maximum baseline in QTcF interval of greater than 30 msec, 60 msec, or 75 msec. Maximum baseline (see Table GPHZ.4.1 for details) will be the maximum non-missing observation in the baseline period. The maximum value during the treatment period will be analyzed. Scheduled and unscheduled measurements will be included.

Table GPHZ.4.6.	Selected Categorical	Limits for ECG Data
-----------------	----------------------	----------------------------

	Low		High	
Parameter	Males	Females	Males	Females
Heart Rate	<50 and decrease	<50 and decrease	>100 and increase	>100 and increase
(bpm)	≥15	≥15	≥15	≥15
PR Interval	<120	<120	>220	>220
(msec)	<120	<120	≥220	≥220
QRS Interval	<00	<00	>120	>120
(msec)	<60	<60	≥120	≥120
QTcF	<330	<340	>450	>470
(msec)	\330	\340	~430	<del>~4</del> /0

Abbreviations: bpm = beats per minute; ECG = electrocardiogram; PR = pulse rate; QTcF = Fridericia's corrected OT interval.

#### 4.5.3.6. Clinical Laboratory Evaluation

Descriptive summaries by treatment and by nominal visit, will be provided for the baseline and postbaseline values, as well as the change from baseline values. The associated descriptive will be presented in SI units and in CN units. Limits from the performing laboratory will be used to define low and high.

Observed and change from baseline values for each visit may be displayed in plots for participants who have both a baseline and at least 1 postbaseline planned measurement. Baseline will be the last non-missing observation prior to taking first study drug. Unplanned measurements will be excluded from plots.

A shift table will be provided including unscheduled measurements. The shift table will include the number and percentage of participants within each baseline category (low, normal, high, or missing) versus each postbaseline category (low, normal, high, or missing) by treatment. The proportion of participants shifted will be compared between treatments using Fisher's exact test.

A listing of abnormal findings will be created for laboratory analyte measurements, including qualitative measures. The listing will include participant identification, treatment group, laboratory collection date, study day, analyte name, and analyte finding.

The MMRM model will be used for the analysis during the treatment period including safety follow-up period for the continuous measurements for following lab tests:

- Calcitonin
- eGFR
- UACR
- Hepatic Enzymes (ALT, AST, ALP, TBL and Direct Bilirubin)
- Pancreatic Enzymes (p-amylase and lipase)

# 4.5.4. Patient Narratives

The following are "notable" events, from start of study drug through end of study participation (or data cutoff for the submission if earlier):

- Deaths
- SAEs
- Permanent discontinuations of study treatment due to AEs
- Pregnancy
- Severe MACE
- Severe dehydration
- Severe renal disorder
- Severe hypersensitivity

Patient narratives (participant level data and summary paragraph) will be provided for participants in the enrolled population with at least one notable event.

## 4.5.5. Special Safety Topics

For AESI or special safety topics, the counts and percentages of participants will be summarized by treatment and PT with decreasing frequency. Individual participant level data may be presented. Displays with individual participant level data may be created using various formats, such as a customized listing and/or a customized graphical patient profile. Adverse events of special interest are defined in each section of special safety topics, where applicable.

# 4.5.5.1. Exocrine Pancreas Safety

#### 4.5.5.1.1. Pancreatic Enzyme

Observed pancreatic enzyme data (p-amylase and lipase) will be summarized by treatment. The counts and percentages of participants with maximum postbaseline pancreatic enzyme value exceeding the following thresholds will be provided by baseline pancreatic enzyme value ( $\leq$  ULN, > ULN), and postbaseline:  $\leq$ 1 × ULN, (>1 to  $\leq$ 3) × ULN, (>3 to  $\leq$ 5) × ULN, (>5 to <10) × ULN, >10 × ULN.

Mean change for pancreatic enzymes may be evaluated using an MMRM model with log transformed (postbaseline measure/baseline measure), as response variable will be used to analyze each pancreatic enzyme.

#### 4.5.5.1.2. Pancreatitis Events

Summaries of adjudicated and investigator-reported pancreatic events will be provided by treatment. Detailed searching criteria can be found in Appendix 6 (Section 6.6).

Treatment emergent adjudication-confirmed pancreatitis will be considered as an AESI. Listing of participants with adjudicated pancreatitis may be provided if deemed necessary.

#### 4.5.5.2. Gastrointestinal Adverse Events

## 4.5.5.2.1. Nausea, Vomiting, Diarrhea and Constipation

Summaries and analyses for incidence and severity of following events will be provided by each treatment group:

- Nausea
- Vomiting (including "vomiting" and "vomiting projectile")
- Diarrhea (including "diarrhea" and "diarrhoea")
- Constipation
- 3 events (nausea, vomiting and diarrhea) combined
- 4 events (nausea, vomiting, diarrhea and constipation) combined

Summary of the prevalence over time will also be presented. Time to the onset of nausea, vomiting, and diarrhea will be plotted.

#### 4.5.5.2.2. Severe Gastrointestinal Events

Severe GI AEs (GI SOC) will be captured with AE-CRF form and serious cases will be captured with the SAE form. The PTs in the GI SOC MedDRA version at the time of database lock will be used to identify GI AEs, and only the PTs with serious/severe treatment-emergent cases will be considered as AESIs.

The counts and percentages of participants with severe/serious treatment-emergent GI events will be summarized by treatment.

#### 4.5.5.3. Hepatobiliary Disorders

#### 4.5.5.3.1. Hepatic Events

Severe/serious treatment-emergent hepatic events will be considered as AESI and summarized. The counts and percentages of participants with treatment-emergent potentially drug-related hepatic events will be summarized by treatment using the MedDRA PTs. Detailed searching criteria can be found in Appendix 6 (Section 6.6).

#### 4.5.5.3.2. Acute Gallbladder Disease

Events related to acute gallbladder disease will also be summarized by treatment groups by PT with decreasing frequency. Detailed searching criteria can be found in Appendix 6 (Section 6.6).

#### 4.5.5.3.3. Liver Enzymes

Common analyses for laboratory analyte measurements described in Section 4.5.3.6 are applicable for the liver enzyme related measurements. This section provides additional analyses for liver enzymes.

The counts and percentages of participants with the following elevations in hepatic laboratory tests at any time during the treatment period, and during the entire study including follow up period, will be summarized between treatment groups:

- The counts and percentages of participants with an ALT measurement ≥3 times (3 ×), 5 times (5 ×), and 10 times (10 ×) the central lab ULN will be summarized for all participants with a postbaseline value and for subsets based on various levels of baseline value.
  - o participants whose non-missing maximum baseline value is  $\leq 1 \times ULN$
  - o participants whose maximum baseline is  $>1 \times ULN$ , and
  - o participants whose baseline values are missing.
- The counts and percentages of participants with an AST measurement ≥3 ×, 5 ×, and 10 × the central lab ULN will be summarized for all participants with a postbaseline value and for subsets based on various levels of baseline value, as described above for ALT.
- The counts and percentages of participants with a TBL measurement ≥2 × the central lab ULN during the treatment period will be summarized for all participants with a postbaseline value, and subset into 4 subsets:
  - o participants whose non-missing maximum baseline value is  $\leq 1 \times ULN$
  - o participants whose maximum baseline is  $>1 \times ULN$ , but  $<2 \times ULN$
  - o participants whose maximum baseline value is  $\geq 2 \times ULN$ , and
  - o participants whose baseline values are missing.
- The counts and percentages of participants with a serum ALP measurement ≥2 × the central lab ULN during the treatment period will be summarized for all participants with a postbaseline value and for the subsets based on various levels of baseline value, as described above for TBL.

Maximum baseline will be the maximum non-missing observation in the baseline period. The maximum postbaseline value will be the maximum non-missing value from the postbaseline period. Scheduled and unscheduled measurements will be included.

Plot of maximum total bilirubin versus maximum aspartate aminotransferase and maximum total bilirubin versus maximum alanine aminotransferase will be provided.

# 4.5.5.4. Hypoglycemia

The following categories in accordance with the 2020 American Diabetes Association position statement on glycemic targets (ADA 2020) will be defined in the database.

#### **Glucose alert value (Level 1):**

- **Documented symptomatic hypoglycemia** is defined as any time a participant feels that he/she is experiencing symptoms and/or signs associated with hypoglycemia, and has a BG level of <70 mg/dL (<3.9 mmol/L).
- **Documented asymptomatic hypoglycemia** is defined as any event not accompanied by typical symptoms of hypoglycemia, but with a measured BG <70 mg/dL (<3.9 mmol/L).

• **Documented unspecified hypoglycemia** is defined as any event with no information about symptoms of hypoglycemia available, but with a measured BG <70 mg/dL (<3.9 mmol/L).

# **Documented Clinically Significant Hypoglycemia (Level 2):**

- **Documented symptomatic hypoglycemia** is defined as any time a participant feels that he/she is experiencing symptoms and/or signs associated with hypoglycemia and has a BG level of <54 mg/dL (<3.0 mmol/L).
- **Documented asymptomatic hypoglycemia** is defined as any event not accompanied by typical symptoms of hypoglycemia but with a measured BG <54 mg/dL (<3.0 mmol/L).
- **Documented unspecified hypoglycemia** is defined as any event with no information about symptoms of hypoglycemia available but with a measured BG <54 mg/dL (<3.0 mmol/L).

# **Severe Hypoglycemia (Level 3):**

• Severe hypoglycemia is defined as an episode with severe cognitive impairment requiring the assistance of another person to actively administer carbohydrate, glucagon, or other resuscitative actions. These episodes may be associated with sufficient neuroglycopenia to induce seizure or coma. PG measurements may not be available during such an event, but neurological recovery attributable to the restoration of PG to normal is considered sufficient evidence that the event was induced by a low PG concentration.

# Other hypoglycemia categories:

• **Nocturnal hypoglycemia** is defined as any hypoglycemic event that occurs between bedtime and waking.

To avoid duplicate reporting, all consecutive hypoglycemic events occurring within a 1-hour period will be considered as a single hypoglycemic event.

Statistical summaries and analyses will exclude hypoglycemic events occurring after initiation of rescue antihyperglycemic medication. Both the incidence (percent of participants experiencing ≥1 episode) and the rate (episodes/patient/year) of level 2 or level 3 hypoglycemia, and level 3 hypoglycemia will be reported by treatment.

The incidence of hypoglycemic events will be analyzed using logistic regression with treatment and stratification factors as fixed effects. The rate of hypoglycemic episodes per patient year may be analyzed using a generalized linear mixed-effects model assuming the number of hypoglycemic episodes follows a negative binomial distribution with the mean modeled using stratification factors and treatment as fixed effects. A listing of hypoglycemic events will be provided.

If a hypoglycemic event meets the criteria of severe, the event would specifically be collected as an SAE. Serious hypoglycemia is defined by pharmacovigilance criteria and will also be captured with a SAE form.

[figure not shown]
Severe/serious hypoglycemia will be considered as AESIs. The summaries of severe/serious hypoglycemia will be provided by treatment group, if deemed necessary.

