6.7. Management of Incident Diabetes

Participants who develop diabetes during the study will be

- · provided and trained to use a glucometer
- · educated on the signs and symptoms of hypoglycemia and its treatment, and
- provided a diary to record hypoglycemic episodes per Section 10.4.7.1.

Participants will be referred to their usual care provider and provided with a letter showing the study results indicative of diabetes. The decision to further evaluate, to initiate antihyperglycemic therapy, and the choice of antihyperglycemic medication will be at the discretion of the participant's usual care provider, with the exception of use of DPP-4 inhibitors and GLP-1R agonists, which are prohibited in the study. Monitoring for hypoglycemia includes capture of events as defined in Section 10.4.7.1. Date of diagnosis of diabetes will be captured in the electronic case report form (eCRF).

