8.2.6. Special Safety Topics

Adverse events of special interest (AESIs) are AEs which the sponsor specifies as being of special interest based on standard drug registration topics, safety findings from previous studies in development program, potential risks associated with GLP-1 receptor agonists as noted in product labels and published literature, and comorbidities and risk factors prevalent in the studied populations.

AESIs for this program include:

- a) severe hypoglycemia
- b) pancreatitis (adjudicated)
- c) thyroid malignancies and C-cell hyperplasias
- d) major adverse cardiovascular events (adjudicated); includes, but not limited to cardiovascular death, nonfatal myocardial infarction, nonfatal stroke, and hospitalization for heart failure
- e) supraventricular arrhythmias and cardiac conduction disorders
- f) hypersensitivity events
- g) injection site reactions
- h) allergic/hypersensitivity reactions; includes injection site reactions and antidrug antibody (ADA) formation
- i) hepatobiliary disorders
- i) severe GI AEs
- k) acute renal events
- 1) depression, suicidal ideation, or behavior

If "a" to "l" above are reported, sites will be prompted to collect additional details/data.

Please see Appendix 4 (Section 10.4), for detailed information.

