9.4.4. Safety Analyses

Unless specified otherwise, safety assessments will be guided by an estimand comparing safety of tirzepatide doses with placebo irrespective of adherence to study drug. Thus, safety analysis will be conducted using SS.

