# 4.5. Safety Analyses

Unless specified otherwise, safety assessments will be based on the SS (Table GPHZ.3.1). All data collected between randomization and the end date of study participation will be included, regardless of the adherence to study drug.

The statistical assessment of homogeneity of the distribution of categorical safety responses, between tirzepatide doses and placebo, will be conducted using Fisher's exact test, unless specified otherwise.

The mean change from baseline differences among treatments at all scheduled visits will be assessed via an MMRM using REML. Unless specified otherwise, if the safety parameter is assessed at the 72 weeks, then the model will include treatment group, visit and treatment-by-visit interaction and stratification factors as fixed effects, and baseline value of the safety parameter as a covariate. To model the covariance structure within participants, the unstructured covariance matrix will be used. If this model fails to converge, the covariance structures specified in Section 4.3.2.1 will be tested in order until met convergence. If the data does not warrant the MMRM model, then ANCOVA model will be conducted.

For selected safety parameters, time-to-first-event analysis via the Cox-proportional hazards model may be conducted. Participants without the event will be censored at the end of study participation. For participants experiencing the event, the "time-to-first-event" will be the time (in weeks) from first dose to first occurrence of the event.

Where necessary, the rate of events will be analyzed using a generalized linear mixed-effects model, assuming the number of events follow a negative binomial distribution and with treatment as a fixed effect. The logarithm of days during the active treatment period will be adjusted as an offset, to account for possible unequal treatment duration of follow-up among participants.

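### The hypoglycemia tables stop counting events at an undefined 'rescue' medication, leave later non-serious Level 2 events to a listing, and give the rate no matching person-time

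*SAP*

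**What the plan says.** SAP 4.5.5.4, under the other hypoglycemia categories, sets the rule: "Statistical summaries and analyses will exclude hypoglycemic events occurring after initiation of rescue antihyperglycemic medication". The measures affected follow directly: "Both the incidence (percent of participants experiencing ≥1 episode) and the rate (episodes/patient/year) of level 2 or level 3 hypoglycemia", and the same two measures for Level 3 alone. Incidence is analyzed by logistic regression. For the rate, "The rate of hypoglycemic episodes per patient year may be analyzed using a generalized linear mixed-effects model"; no offset or denominator is given there. The section also plans a listing of hypoglycemic events, and a severe/serious summary only if judged necessary.

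The general rules are in SAP 4.5. On data: "All data collected between randomization and the end date of study participation will be included, regardless of the adherence to study drug". On event rates, where such a model is needed: "The logarithm of days during the active treatment period will be adjusted as an offset". The active treatment period is not defined, and nothing is said about stopping the clock at a new medication.

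Protocol 6.5 and 6.7 allow participants who develop diabetes to start glucose-lowering drugs, with two classes prohibited. Protocol 6.7 adds: "Monitoring for hypoglycemia includes capture of events as defined in Section 10.4.7.1". Protocol 10.4.7.1 provides glucometers to everyone who develops diabetes and to others at the investigator's discretion. It sends episodes to a dedicated form and keeps them off the adverse event form unless serious. Protocol 8.2.6 puts "a) severe hypoglycemia" first among the events of special interest.

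**The concern.** The protocol sets out to capture hypoglycemia in participants who develop diabetes, and the SAP then leaves out of its hypoglycemia summaries whatever they experience once treated for it. A reader asking how often Level 2 or Level 3 hypoglycemia occurred when the study drug was combined with another glucose-lowering drug would find no hypoglycemia table that answers.

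The second problem is the rate. If events stop counting at medication start but days do not, person-time in which no event can count stays in the denominator. Starting such a drug happens after randomization, and the protocol's exploratory objective on delayed progression to type 2 diabetes anticipates fewer starts on tirzepatide. The arms could therefore lose unequal amounts of countable time.

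**Working it through.** The plan states no hypoglycemia rate, event count or share starting medication, so there is no planned figure to reproduce. The check has two parts.

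**Where a post-initiation event is reported**

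| Event after medication start | Hypoglycemia incidence and rate | AE/SAE tables | Elsewhere |
|---|---|---|---|
| Level 2, non-serious | Excluded (SAP 4.5.5.4) | Not on the AE form (Protocol 10.4.7.1) | Listing only |
| Level 3 | Excluded (SAP 4.5.5.4) | SAE summary over the whole postbaseline period, no rescue exclusion (SAP 4.5.3.2) | Listings; narrative (SAP 4.5.4) |

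In the incidence model, a participant whose first event follows medication start counts as event-free.

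**What the offset would do to the rate**

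Inputs: a 72-week treatment period (Protocol 4.1); a share f starting medication, at week t (both assumed).

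Share of person-time in which no event can count: d = f × (72 − t)/72.

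Reported rate ÷ rate while off such medication = 1 − d.

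With t = 36, (72 − 36)/72 = 0.5:

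- f = 1%: 1 − 0.005 = 0.995, understated by 0.5%
- f = 5%: 1 − 0.025 = 0.975, by 2.5%
- f = 10%: 1 − 0.05 = 0.95, by 5%
- f = 20%: 1 − 0.10 = 0.90, by 10%

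Varying t from 24 to 52 weeks widens the range. The smallest effect is 0.01 × 20/72 = 0.3%; the largest is 0.20 × 48/72 = 13.3%.

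**Between arms.** Suppose true rates are equal and initiation at week 36 is 10% on placebo and 1% on tirzepatide (assumed). The reported tirzepatide/placebo rate ratio is 0.995/0.95 = 1.047 instead of 1.00.

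**Against a rate that counts every event over all time.** If the event rate on such medication is r times the rate off it (assumed), reported ÷ all-event rate = (1 − d)/(1 − d + r × d). With t = 36:

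- f = 5%, r = 3: 0.975/(0.975 + 0.075) = 92.9%
- f = 5%, r = 10: 0.975/(0.975 + 0.25) = 79.6%
- f = 10%, r = 3: 0.95/(0.95 + 0.15) = 86.4%
- f = 10%, r = 10: 0.95/(0.95 + 0.50) = 65.5%

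**An effect in the other direction.** The Safety Analysis Set includes the 4-week follow-up (SAP Table GPHZ.3.2). If events there count but the offset covers treatment days only, the rate could be overstated, by up to 76/72 = 1.056 at a constant event rate.

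**The case against.** The strongest reply is that the SAP never says it keeps full treatment time for hypoglycemia. Its section gives no offset, the rate model is optional, and the offset in SAP 4.5 is a general rule for use where necessary. That stands: the defect is an unspecified denominator, and the mismatch appears only if the general rule is applied. The rate itself is nevertheless to be reported, so some denominator is needed.

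A reader might infer that severe events after medication start disappear. They do not: they remain in the serious adverse event table, listing and narratives. SAP 6.1.4 also summarizes glucose-lowering drug use after randomization, so the number starting treatment will be visible.

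A reader might also infer a breach of the protocol's safety estimand: "safety assessments will be guided by an estimand comparing safety of tirzepatide doses with placebo irrespective of adherence to study drug". That sentence (Protocol 9.4.4) opens by allowing exceptions, concerns adherence to study drug rather than added medication, and Protocol 9.4.4.3 leaves special-interest analyses to the SAP. The exclusion is permitted.

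Finally, separating these events can be defended. Glucometers go to everyone who develops diabetes, so detection rises after diagnosis, possibly more often on placebo. An all-events comparison carries that difference and the effects of the other drugs. This stands as a reason to show both versions; it does not justify leaving non-serious Level 2 events untabulated.

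**Conclusion.** The concern holds in a limited form. Non-serious Level 2 events after an undefined rescue medication would have no summary table, and Level 3 events would be missing from the hypoglycemia analyses though reported elsewhere. The rate has no stated denominator, and the only offset available would understate the rate off such medication by about 0.5% to 10%, assuming 1% to 20% start at week 36.

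Two stronger readings are not supported. The text does not fix the net direction of error, because follow-up events counted over treatment days would push the rate up. Nor does the offset necessarily favor tirzepatide: with more initiation on placebo, it moves the ratio against tirzepatide. That these are the highest-risk events is plausible, but the documents hold no data on it. Every size above rests on assumed initiation shares, timing and rate multiples.

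**What to change.** In SAP 4.5.5.4:

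- Define rescue antihyperglycemic medication as any antihyperglycemic drug started for incident diabetes.
- Add by-arm incidence and rate tables, for Level 2 or 3 and for Level 3, on the Safety Analysis Set, including all events regardless of such medication.
- In the version that excludes later events, end each participant's exposure and offset at the medication start date.
- State the denominator for every rate, and make the event window and person-time window match, including whether the 4-week follow-up is in both or neither.

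Listing the exclusion and its rationale in SAP 4.9 would help transparency but is not the substance of the change.

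The cost is SAP wording and one extra set of tables. The all-events tables need a note that glucometer use increases after a diabetes diagnosis.
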